5.4.5 Final Study Visit

The final study evaluation will be two visits (as above in the visit table) with the first visit occurring 12 months after study enrollment. See appendix for the study calendar of study endpoints and evaluations.

During the 12-month visit, participants will be informed of their treatment assignments, final weight, clinic and 24-hour blood pressures, and body mass index. Additional data from the 12-month visit will not be analyzed in time to be provided to the participant.

Additional follow-up for adverse or serious adverse events will continue for 30-days after the final 12-month visit with one telephone follow-up by the research team. The participant will be responsible for scheduling any additional clinic visits and medical care for adverse or serious adverse events.

6 Study Analysis

6.1 Sample Size Determination

For Aim 1, approximately 930 individuals will be screened to get to a total of 340 enrolled participants (170 participants per randomized arm). This is designed under the assumption that there will be a further 15% dropout rate at the 6-month mark following randomization, to result in an effective sample size of 264.¹⁸⁴ In Nidich et al.,¹⁸⁵ the 3-month transcendental meditation program showed a mean difference of 6.3 and 4.0 in systolic and diastolic blood pressure change with a standard deviation of 13.6 and 9.7, respectively, as compared to a case of usual control among young adults at hypertension risk. With an effective sample size of 264, there is power of 0.94 and 0.87 for systolic and diastolic blood pressure, respectively, each at a two-tailed 0.025 test for an overall significance level of 0.05. For Aim 2, the effective sample size of 264 subjects will provide 90% power to detect a difference in the population mean difference from baseline to 6 months between treatment groups of about 0.4 standard deviations of the differences (moderate effect size). Aim 3 is an exploratory aim.

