3.1.3 Primary Safety Endpoints

- Number and type of adverse events
- Number and type of serious adverse events
- Subject Withdrawal rate and reason

4 Study Subjects – Enrollment and Withdrawal

See Appendix for accrual expectations by research site

The recruitment and screening protocol will be the same at both sites. The accrual goal is 340 participants total (n=170 per arm) over 25 months of recruitment. Participants will be randomized to control or intervention arms at each site.

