4.4.2 Recruitment and Retention Strategies

See appendix for expected numbers of women and minorities to be recruited.

The site coordinators will mail an introductory research packet to patients who have been identified by each electronic health record system as potentially eligible, based upon the WCHQ or ICD 10 diagnosis code R03.0 criteria described above. The packet will include an introductory letter, a flyer summarizing the MyHEART research project, a magnet, bookmark and a pre-paid opt-out postcard. The packet will only be mailed once to the home address listed within the electronic health record system. If a participant contacts us independently and requests a packet, it will be mailed to the address that is provided by them. If an opt-out response is not received after 2 weeks, a research staff member will call patients to perform telephone screening to assess eligibility based on inclusion and exclusion criteria; research staff at UW_Madison will be calling all Madison participants and research staff at Aurora Health Care will be calling all Milwaukee participants (telephone scripts for each site are uploaded to ARROW). The telephone screening for Aurora Health Care participants will also include a question to obtain verbal authorization that the participants give verbal permission for Aurora Health Care research staff to send their information to the University of Wisconsin-

Madison research staff for data entry. At the completion of the telephone screening, the patient will be subsequently invited for a face-to-face visit at the research clinic within their medically homed region (Madison or Milwaukee). We will recruit a total of 340 participants over 25 months. We anticipate an accrual rate of 12-13 eligible participants per month. We estimate having to screen approximately 930 potentially eligible participants.

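### Section 6.1: 340 enrolled with 15% dropout leaves 289, not 264 (a conservative slip); separately, 12-13 per month for 25 months gives 300-325, not 340

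*Combined protocol and SAP*

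**What the plan says.** Section 6.1 gives the recruitment path as "approximately 930 individuals will be screened to get to a total of 340 enrolled participants (170 participants per randomized arm"). It then allows for "a further 15% dropout rate at the 6-month mark following randomization, to result in an effective sample size of 264". The planning effects come from a cited meditation trial, which "showed a mean difference of 6.3 and 4.0 in systolic and diastolic blood pressure change". The standard deviations, 13.6 and 9.7, are taken from the same trial. From these it concludes: "With an effective sample size of 264, there is power of 0.94 and 0.87 for systolic and diastolic blood pressure, respectively". The type I error is split between the two outcomes, "each at a two-tailed 0.025 test for an overall significance level of 0.05". Aim 2 uses the same 264, for 90% power at about 0.4 standard deviations, with no significance level stated.

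On recruitment, section 4 says: "The accrual goal is 340 participants total (n=170 per arm) over 25 months of recruitment". Section 4.4.2 repeats 340 over 25 months and adds: "We anticipate an accrual rate of 12-13 eligible participants per month".

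**The concern.** The enrolled number, the dropout rate and the effective size in section 6.1 are linked by a single multiplication, and the product is not the figure given. Every power statement in that section rests on 264, so a reader will want to know where it comes from.

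Power is not what is at stake, because 264 is smaller than the number the stated dropout would leave. The difficulty is that the planned loss cannot be read off. At an actual loss of, say, 20% by 6 months, retention would be worse than a 15% plan but within a 22% plan. The monitoring committee may ask for interim power (section 6.3) and reviews actual against projected accrual (section 8.6). It needs one dropout assumption and one accrual forecast to compare against.

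**Working it through.** **Inputs.** From section 6.1: 340 enrolled, 170 per arm; 15% dropout; effective size 264, or 132 per arm; differences 6.3 and 4.0 mmHg; standard deviations 13.6 and 9.7; two-sided 0.025 per outcome. From sections 4 and 4.4.2: 340 in 25 months, at 12-13 per month.

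**1. The plan's own power figures.** For n per arm, the normal approximation is power = Φ(d / (s·√(2/n)) − 2.241), where 2.241 is the normal quantile for two-sided 0.025. At n = 132, √(2/n) = 0.1231.

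- Systolic: 6.3/13.6 = 0.4632; 0.4632/0.1231 = 3.763; less 2.241 = 1.522; power 0.936.
- Diastolic: 4.0/9.7 = 0.4124; 0.4124/0.1231 = 3.350; less 2.241 = 1.109; power 0.866.

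These round to the stated 0.94 and 0.87. Noncentral t gives 0.934 and 0.863.

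**2. The effective size.**

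- 340 × (1 − 0.15) = 289, which is 25 more than 264.
- 264/340 = 0.776, so 264 corresponds to 22.4% loss.
- 264/0.85 = 310.6, so about 311 enrolled at 15% loss.

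Other routes from the stated inputs also miss 264: 340/1.15 = 295.7, and 15% taken twice gives 340 × 0.85² = 245.7. Taking 15% and then a further 10% gives 260.1, still not 264, and it needs a loss the protocol does not state.

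**3. Power if 15% dropout applies to 340.** With 289 evaluable, n = 144.5 per arm and √(2/n) = 0.1176.

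| Evaluable | Method | Systolic | Diastolic |
|---|---|---|---|
| 264 | Normal | 0.936 | 0.866 |
| 264 | Noncentral t | 0.934 | 0.863 |
| 289 | Normal | 0.955 | 0.897 |
| 289 | Noncentral t | 0.953 | 0.894 |

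**4. Aim 2.** The difference detectable with 90% power, in standard deviations, is (z for alpha + 1.282) × √(4/N). Section 6.1 states no alpha for Aim 2, so both candidates are shown.

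| Two-sided alpha (assumed) | N = 264 | N = 289 |
|---|---|---|
| 0.05 | 3.242 × 0.1231 = 0.40 | 3.242 × 0.1176 = 0.38 |
| 0.025 | 3.523 × 0.1231 = 0.43 | 3.523 × 0.1176 = 0.41 |

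**5. Accrual.**

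- 12 × 25 = 300 and 13 × 25 = 325, so 340 is missed by 40 or by 15.
- 340 in 25 months needs 340/25 = 13.6 per month.
- At the stated rate, 340 takes 340/13 = 26.2 to 340/12 = 28.3 months.

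If recruitment closed at 25 months, 15% dropout would leave:

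| Enrolled | Evaluable | Systolic power | Diastolic power |
|---|---|---|---|
| 300 | 255 | 0.93 | 0.85 |
| 325 | 276 | 0.95 | 0.88 |

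**The case against.** The strongest reply is that this is editorial. The target of 340 is the same wherever it appears. Take 340 with 15% and power is better than stated; take 340 with 264 and it is exactly as stated. That is right, and it limits the point to clarity of the planning assumptions.

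A second reply is that the word used to introduce the dropout signals an additional loss. It most naturally means loss after the step from 930 screened to 340 enrolled. The dropout is placed after randomization, and 340 is the number randomized. Sections 2.5.4 and 4.7.2 do provide for mandatory withdrawals after enrolment, for example on pregnancy, but give no rate, so they cannot account for 264.

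Third, calling the slip conservative presumes that 264 is the wrong figure, and the protocol does not show which of the three is wrong. That stands. The description is accurate only if 340 and 15% are both kept, and it does not extend to the accrual shortfall, whose low end falls slightly below the stated power. The two mismatches may also share a cause: 311/25 = 12.4 per month, inside the forecast range, which would fit an enrolment figure of about 311 that was not updated to 340. Nothing in the protocol confirms this.

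Fourth, the accrual rate is an approximate forecast; 13.6 is about 5% above its upper end, and a correction has little operational value in a protocol that already carries May 2022 data-transfer text. This is fair, and the accrual point is the lesser of the two. The accrual-by-site appendix cited in section 4 was not available for this check.

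Finally, all these power figures treat completers as an unadjusted two-sample comparison, whereas section 6.2 plans intention to treat with multiple imputation and analysis of covariance. That applies equally to the protocol's own figures and does not affect the dropout arithmetic.

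**Conclusion.** The statement in section 6.1 is wrong as written: 340, 15% and 264 cannot all hold, and no section examined supplies another quantified loss that closes the gap of 25. The power figures are right, conditional on 264. With 289 evaluable they rise by about 0.02 (systolic) and 0.03 (diastolic), so power is not threatened. The Aim 2 detectable difference barely moves.

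The accrual forecast is also inconsistent with its target, by 15-40 participants or roughly 1-3 months. Even if recruitment stopped at 25 months, power would stay within about 0.02 of the stated values.

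These conclusions rest on 1:1 allocation, the stated effects and standard deviations, two-sided 0.025 per co-primary outcome, and an unadjusted comparison of completers. The 0.40 and 0.38 standard deviations for Aim 2 also assume two-sided 0.05.

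**What to change.** Return to the sample-size calculation, establish which figure is out of step, and put one consistent set in section 6.1:

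- **(a)** 340 enrolled, 15% dropout, 289 evaluable, power about 0.96 and 0.90 (normal approximation, whose values at 264 round to the stated ones; 0.95 and 0.89 by noncentral t), and an Aim 2 detectable difference of about 0.38 standard deviations at two-sided 0.05; or
- **(b)** keep 264, the power of 0.94 and 0.87 and about 0.4 standard deviations, and say that this allows for about 22% loss from 340. This is suitable only if that loss is what the sponsor means to plan for, since the protocol currently states 15%.

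It would help to name the power method and the Aim 2 significance level in the same edit. In sections 4 and 4.4.2, align the forecast with the target: about 13.6 per month for 25 months, or about 26-28 months at 12-13 per month.

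The cost is a text correction in three places. The enrolment target and the analysis do not change.

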6.2 Statistical Methods

See Appendix for the full Statistical Analysis Plan (SAP)

Statistical Analysis Plan Overview:

Data will be analyzed by intent to treat. Missing data will be imputed using multiple imputations.

For Aim 1, the comparisons for the primary outcomes of systolic and diastolic blood pressure change from baseline to 6 months will be done using analysis of covariance. The primary comparisons for the secondary outcome of hypertension control at 6 months will be based on Fisher's exact tests. Sequential hypothesis testing will also be performed. The 12-month analysis will focus on *maintenance* of behavior change, to assess whether significant differences seen between baseline and 6 months are retained. We will also assess the differential effectiveness of the intervention across subgroups by developing exploratory regression models.

For Aim 2, behavioral outcomes will be analyzed in a similar manner as with the clinical outcomes in Aim 1 depending on whether they are continuous or categorical. Analyses (t-tests or Wilcoxon tests and ANCOVA for continuous variables; Fisher's exact test for the categorical variable) will be performed for differences from baseline to 6 months between treatment groups. Linear or generalized linear mixed-effects regression models will be fit to describe longitudinal behavioral measurements over time.

For Aim 3, analyses will examine hypothesized mediators of the MyHEART intervention (for example, autonomy support, internal motivation, perceived competence, and patient activation). We will estimate mediation effects in multilevel models¹⁸⁶⁻¹⁹⁰ where mediation is assessed by fitting two models. Standard errors and 95% confidence intervals for the mediation effect and percent-mediated estimates will be calculated. This analysis will be pivotal to guide future replication and dissemination of MyHEART.

6.3 Planned Interim Analysis:

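### The only explicit alpha rule for the two co-primary outcomes is a fixed 0.025/0.025 split; Holm's step-down would keep the 0.05 family-wise error with more power, and the sequential testing named in 6.2 should be defined as that rule

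*Combined protocol and SAP*

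**What the plan says.** Section 6.1 takes from a published trial of a different intervention "a mean difference of 6.3 and 4.0 in systolic and diastolic blood pressure change"; the SDs it pairs with these are 13.6 for SBP and 9.7 for DBP. For 264 evaluable participants the stated power is 0.94 for SBP and 0.87 for DBP. The level behind both figures is given as "each at a two-tailed 0.025 test for an overall significance level of 0.05". That is a Bonferroni split.

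Section 6.2 analyses both outcomes at 6 months by analysis of covariance and gives no alpha per test. After naming Fisher's exact test for hypertension control it adds: "Sequential hypothesis testing will also be performed". It does not say which hypotheses are in the sequence, in what order, or at what level. It describes the 12-month analysis as one of maintenance, and refers to an appendix for the full SAP. That appendix is not among the supplied documents.

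The Study Summary also places the primary comparison at 6 months. Section 3.1.1 attaches the co-primary outcome to both 6 and 12 months. No section supplied says whether success needs one of the two outcomes or both.

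**The concern.** Under a fixed split each outcome is tested at 0.025 whatever happens on the other. If SBP is clearly positive and the DBP p-value lies between 0.025 and 0.05, the DBP conclusion is lost, although a step-down rule with the same family-wise error would allow it. DBP has the lower planned power, so it is the outcome more exposed. The hypothesis in 2.2 is a fall in both pressures, so the chance of showing both matters to the trial's own aim.

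The sentence on sequential testing does not settle this. It could mean a step-down between SBP and DBP, a gate from blood pressure to hypertension control, or something else. Undefined, it leaves the choice open until after the data are seen.

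**Working it through.** **Inputs.** From 6.1: differences 6.3 (SBP) and 4.0 (DBP) mmHg; standard deviations 13.6 and 9.7; 264 evaluable; alpha 0.025 two-sided each. From 5.2: equal allocation, so 132 per arm. Assumed: SBP-DBP correlation of the test statistics, since the documents give none; main range 0.4 to 0.8, wider range 0 to 0.9.

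**Step 1. Reproduce the stated power.** Expected test statistic m = difference / (SD × √(2/n)), with n = 132 and √(2/132) = 0.1231.
- SBP: 6.3 / (13.6 × 0.1231) = 3.763
- DBP: 4.0 / (9.7 × 0.1231) = 3.350

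Power is close to Φ(m − c), where c = 2.241 for two-sided 0.025 and 1.960 for two-sided 0.05.

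| Outcome | Stated | At 0.025 | At 0.05 |
|---|---|---|---|
| SBP | 0.94 | Φ(1.522) = 0.936 | Φ(1.803) = 0.964 |
| DBP | 0.87 | Φ(1.109) = 0.866 | Φ(1.390) = 0.918 |

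The stated figures reproduce at 0.025 and not at 0.05, so they do rest on the split. The two levels sum to 0.025 + 0.025 = 0.05.

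**Step 2. Apply Holm to the same two tests.** Test the smaller p-value at 0.025; if it is significant, test the other at 0.05. Then:
- P(DBP rejected) = P(|Z_D| > 2.241) + P(|Z_S| > 2.241 and 1.960 < |Z_D| ≤ 2.241), and the same with the outcomes exchanged for SBP.
- P(at least one rejected) is unchanged, because the first step is the same 0.025 threshold.

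Bivariate normal probabilities at 132 per arm (simulated, and confirmed by numerical integration):

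| Correlation (assumed) | SBP: split → Holm | DBP: split → Holm | Both: split → Holm | At least one (same under either) |
|---|---|---|---|---|
| 0.4 | 0.936 → 0.956 | 0.866 → 0.911 | 0.825 → 0.890 | 0.977 |
| 0.6 | 0.936 → 0.952 | 0.866 → 0.909 | 0.836 → 0.895 | 0.966 |
| 0.8 | 0.936 → 0.946 | 0.866 → 0.908 | 0.850 → 0.902 | 0.952 |

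Over correlations 0 to 0.9, DBP under Holm is 0.908 to 0.915, and both outcomes go from 0.811-0.859 to 0.884-0.907.

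**Step 3. Check the error rate.**
- Both nulls true: family-wise error 0.049 to 0.036 over correlations 0 to 0.9, identical under the two rules.
- SBP effective, DBP null: false rejection of DBP is 0.025 under the split and 0.049 to 0.040 under Holm.

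Holm stays at or below 0.05 in each case. The split leaves half of the allowance unused in the second.

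**Step 4. Sensitivity to the sample size.** Section 6.1 also gives 340 enrolled and 15% dropout, and 340 × 0.85 = 289, not 264. At 289 (144.5 per arm) and correlation 0.4 to 0.8, DBP goes from 0.897 to 0.932-0.934, and both outcomes from 0.87-0.88 to 0.92-0.93. The gain is a little smaller but does not depend on the 264.

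**The case against.** - **The split is a planning assumption.** It appears only in the sample-size section. Powering at the stricter level and analysing with a step-down rule is compatible with 6.1 and 6.2 together, and the full SAP may already say so. This stands. A reader might infer that the final tests are fixed at 0.025 each; the documents do not establish that. They do not establish the reverse either.
- **Bonferroni is valid and both stated powers are at least 0.87.** This stands. The point is efficiency, and no conclusion reached under the split would be unsound.
- **Holm is not entirely free.** This stands in part. The chance of at least one significant result does not move, false rejection of an ineffective DBP rises within the 0.05 limit, and matching simultaneous intervals are harder to give.
- **The success rule is not stated.** If both outcomes had to be significant, each could be tested at 0.05 without any split, giving 0.89-0.91 for both at correlation 0.4 to 0.8. Holm would then be unnecessary, but the fixed split would be wasteful all the same. An overall 0.05 built from two 0.025 tests fits a plan in which either outcome can succeed alone.
- **The family may be larger than two.** Section 3.1.1 brings in 12 months, and the hypothesis in 2.2 names both clinic and ambulatory pressures. A two-test Holm controls error only for the family it is applied to, so the family must be stated with the rule. This stands and is built into the fix.

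**Conclusion.** The concern holds as an efficiency point. The only explicit alpha rule in the supplied text is a valid fixed split that Holm improves on at the same family-wise error, and the one sentence that might announce such a procedure does not define it. At 264 evaluable participants, under the plan's own effects and standard deviations, Holm gains about 4 points of power for DBP, 1 to 2 for SBP and 5 to 6 for both outcomes together. The size rests on an assumed correlation of 0.4 to 0.8 and on a primary family of the two 6-month tests.

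A stronger reading would be that the plan's multiplicity control is faulty, or that Holm costs nothing. Neither is supported: error is controlled under the split, and Holm does not raise the chance of at least one positive result and complicates the intervals.

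**What to change.** State in 6.1 and 6.2, before any unblinded analysis:
1. The primary family is the change from baseline to 6 months in SBP and in DBP. The 12-month comparisons are maintenance analyses outside this family; align 3.1.1 with this. Say which blood pressure measurement, clinic or ambulatory, supplies the two tests.
2. The smaller of the two p-values is tested at 0.025 two-sided. If it is significant, the other is tested at 0.05 (Holm). A significant result on either outcome is a positive finding for that outcome.
3. Hypertension control at 6 months is tested at 0.05 only if both blood pressure hypotheses are rejected.
4. Sequential testing means this procedure and nothing else. If the SAP appendix already holds a step-down rule, bring the two sections into line with it.

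Keep 0.94 and 0.87 as conservative planning figures.

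**Cost:** a few sentences, with no added participants, visits or data. The drawback is that simultaneous confidence intervals matching Holm are less simple. Report 97.5% intervals as a conservative companion, and note that such an interval can include zero for an outcome rejected at the second step.

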6.2 Statistical Methods

See Appendix for the full Statistical Analysis Plan (SAP)

Statistical Analysis Plan Overview:

Data will be analyzed by intent to treat. Missing data will be imputed using multiple imputations.

For Aim 1, the comparisons for the primary outcomes of systolic and diastolic blood pressure change from baseline to 6 months will be done using analysis of covariance. The primary comparisons for the secondary outcome of hypertension control at 6 months will be based on Fisher's exact tests. Sequential hypothesis testing will also be performed. The 12-month analysis will focus on *maintenance* of behavior change, to assess whether significant differences seen between baseline and 6 months are retained. We will also assess the differential effectiveness of the intervention across subgroups by developing exploratory regression models.

For Aim 2, behavioral outcomes will be analyzed in a similar manner as with the clinical outcomes in Aim 1 depending on whether they are continuous or categorical. Analyses (t-tests or Wilcoxon tests and ANCOVA for continuous variables; Fisher's exact test for the categorical variable) will be performed for differences from baseline to 6 months between treatment groups. Linear or generalized linear mixed-effects regression models will be fit to describe longitudinal behavioral measurements over time.

For Aim 3, analyses will examine hypothesized mediators of the MyHEART intervention (for example, autonomy support, internal motivation, perceived competence, and patient activation). We will estimate mediation effects in multilevel models¹⁸⁶⁻¹⁹⁰ where mediation is assessed by fitting two models. Standard errors and 95% confidence intervals for the mediation effect and percent-mediated estimates will be calculated. This analysis will be pivotal to guide future replication and dissemination of MyHEART.

6.3 Planned Interim Analysis:

There is no interim analysis planned. However, we are prepared, if requested by the Data Safety and Monitoring Committee at any point, to calculate interim statistical power for its review. Projections of interim power can be made under several scenarios for future data, including assumptions that current trends continue or that the future data reflect the relative effects used in the design of the trial. Safety reports will tally adverse events by intervention assignment and postulated relationship to the trial interventions; event rates will be reported per person year of follow-up. Should excessive risk to study participants be determined during the data safety monitoring review, the study will

be stopped and all participants notified in a manner appropriate to the nature of the risk as defined by the IRB and DSMB.

7 Data Collection, Handling, and Record Keeping

